The secondary efficacy objective is to evaluate whether administration of CAP-1002 by intracoronary infusion may result in other left ventricular structural or functional cardiac benefits for subjects with ischemic left ventricular dysfunction and a previous MI. Also evaluations will investigate whether administration of CAP-1002 may result in clinical or biomarker benefits for subjects with ischemic left ventricular dysfunction and a previous MI.

Study Design:

In Phase 2, the Primary Randomized Cohort will enroll up to approximately 103 subjects with a previous myocardial infarction (MI) and resultant ischemic left ventricular dysfunction meeting all inclusion and no exclusion criteria. The Primary Randomized Cohort will include the Recent and Chronic MI strata (n= approximately 51-52 per stratum). These 103 subjects will be randomized in a double-blind fashion to receive either CAP-1002 or placebo (collectively referred to as Investigational Product [IP]) in a 2:1 ratio favoring CAP-1002 to achieve up to 93 subjects with complete 12 month data (assumes 10% non-completion rate and 103 subjects randomized). After completion of the screening procedures and meeting all inclusion and exclusion criteria, study subjects will be randomized to receive CAP-1002 or placebo administered via intracoronary infusion. All subjects in the Primary Randomized Cohort will be followed at week 2 and at months 1, 3, 6 and 12 after planned CAP-1002 or placebo infusion. Efficacy will be assessed at all specified post-infusion visits, with the 12 month visit being the primary efficacy endpoint. An administrative interim analysis of the final 6 month data will be performed when all subjects in the Primary Randomized Cohort have completed the 6 month visit to assist in planning Phase III studies.

The double-blind, placebo-controlled design of the Primary Randomized Cohort will maximize

the study's ability to assess both safety and efficacy, as both may be subject to bias from the perspective of Investigators and subjects.

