### 2.3.5 Primary Efficacy Hypothesis

The primary efficacy hypothesis is that CAP-1002 is superior to placebo in reducing infarct size in either all subjects combined (“full group”) or in subjects with recent MI (“subgroup”). A closed testing procedure will be used so that strong control of type 1 error is maintained. Specifically, the following hypothesis sets will be tested:

$$1) \quad H_{0,s}: \mu_{c,s} - \mu_{p,s} = 0 \quad \text{or} \quad H_{0,f}: \mu_{c,f} - \mu_{p,f} = 0 \\ H_{a,s}: \mu_{c,s} - \mu_{p,s} < 0 \quad H_{a,f}: \mu_{c,f} - \mu_{p,f} < 0$$

and

$$2) \quad H_{0,s} \cap H_{0,f}: \mu_{c,s} - \mu_{p,s} = 0 \text{ and } \mu_{c,f} - \mu_{p,f} = 0 \\ H_{a,s} \cap H_{a,f}: \mu_{c,s} - \mu_{p,s} < 0 \text{ or } \mu_{c,f} - \mu_{p,f} < 0$$

where  $s$  denotes the subgroup,  $f$  denotes the full group,  $\mu_{c,s}$  and  $\mu_{p,s}$  are mean percent changes in the CAP-1002 and placebo treatment groups, respectively, in the subgroup, and  $\mu_{c,f}$  and  $\mu_{p,f}$  are mean percent changes in the CAP-1002 and placebo treatment groups, respectively, in the full group.

Therefore, both the intersection null hypothesis ( $H_{0,s} \cap H_{0,f}$ ) and either of the individual null hypotheses ( $H_{0,s}$  or  $H_{0,f}$ ) must be rejected at the (one-sided) 0.025 significance level for the trial to be declared a success. In other words, the null hypothesis of “no treatment effect in the full group and no treatment effect in the recent MI subgroup” must be rejected at the one-side 0.025 significance level, necessarily meaning that either the result is significant in the full group, in the recent MI subgroup, or both. The results of the tests of the individual hypotheses (also at the one-sided 0.025 significance level) determines which specific comparisons are significant.

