## 9. EFFICACY ANALYSIS

All efficacy parameters will be listed for the primary ITT population and summarized for the mITT population. The primary analysis of primary and secondary efficacy endpoints will be done using the primary mITT population. Secondary analyses may be done using the other analysis populations defined in [Section 6](#) or in subgroups defined in [Section 7.4](#). In addition, “last observation” analyses will be done for certain parameters for which some subjects’ final assessments were done too late to be included in the Month 12 analysis window.

Analyses of changes from baseline will be done using general linear models with baseline values as covariates. Analyses of the effect of treatment group, analysis window (e.g., baseline, Month 6, Month 12), and their interaction will be done using mixed effects linear regression, with subject as a random effect, analysis window, and treatment group as fixed effects, and baseline as a fixed-effect covariate. For “last observation” analyses, “time” as a continuous covariate will be substituted for analysis window. Study site may also be included as a random effect if there is evidence of correlation within study sites (per the interclass correlation coefficient from the unconditional model) and/or if doing so appreciably improves the model fit (e.g., per Akaike’s Information Criterion). Other covariates that may be considered include age (< 65 vs.  $\geq$  65 years), sex, race (African-American vs. other), baseline 6MWT, baseline LVESV, baseline NT-proBNP, and DSA (as an indicator variable). Residuals will be evaluated for substantial departure from normality and independent and constant variance and appropriate remedies (e.g., data transformations, detecting and assessing the influence of outliers, alternative analytical approaches) will be attempted when necessary. An unstructured covariance will be the default covariance structure but other structures (e.g., compound symmetry) may be used to evaluate sensitivity to the choice of structure or, if study site is included as a random effect, to achieve convergence.

Assuming missing observations are “missing at random” (MAR), i.e., the fact that they are missing is unrelated to the missing variable but can be related to another variable on which data have been collected, the maximum likelihood (ML) approach is able to handle subjects with

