either Month 6 or Month 12 changes from baseline missing, but not both. Therefore, for analyses based on the mITT population, missing data will be addressed using ML. For analyses based on the ITT population, in which some subjects may have both Month 6 and Month 12 changes from baseline missing, multiple imputation will be used based on all observations and will use a fully conditional specification method with 20 burn-in iterations and the regression method of imputation. Variables in the imputer's model will be baseline observation (because baseline is used as a covariate in analyses), Month 6 change from baseline, Month 12 change from baseline, and treatment group. Because the MAR assumption is not testable, and because it seems possible that subjects with poorer outcome may be more likely to miss trial assessments, a sensitivity analysis under a "missing not at random" (MNAR) assumption will be done (for the final analysis only) of the primary efficacy endpoint in which multiple imputation will use the pattern-mixture model approach to address missing values; i.e., the imputation will be based on a pre-specified subset of subjects. For this MNAR analysis, only those subjects who had implantable cardioverter defibrillators (ICDs) inserted during the trial. Because very few missing observations are expected in this trial, 5 imputed data sets will be used for all analyses using multiple imputation.

A closed testing procedure will be used for the primary efficacy analysis only (see [Section 2.3.5](#)) and will be done as follows:

1. Let  $p_f$  and  $p_s$  be the p-values from the tests of the individual null hypotheses involving the full group and the subgroup, respectively; tests will be based on least squares (LS) means comparisons.
2. Let  $t_{max} = \max(t_f, t_s)$ , where  $t_f$  and  $t_s$  are the t-statistics from the full group and subgroup analyses in (1) above.
3. Let  $r$  = the correlation between  $t_f$  and  $t_s$ , estimated by the ratio of SDs of the treatment effect estimates in the full group and subgroup.
4. Let  $p_{inter}$  be the p-value from the test of the intersection hypothesis using Dunnett's test; specifically,  $p_{inter} = 1 - \text{probnorm}(t_{max}, t_{max}, r)$ .

Then, if  $p_{inter} < 0.025$  and either  $p_f < 0.025$  or  $p_s < 0.025$  (with treatment effect favoring CAP-1002), the test of treatment effect for the primary efficacy endpoint will be considered statistically significant.

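### SAP Section 9 refers t-statistics to a normal distribution, so the primary test's family-wise error is about 2.7% to 2.9%, not the promised one-sided 2.5%

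*SAP*

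**What the plan says.** SAP Section 2.3.5 sets the standard: "A closed testing procedure will be used so that strong control of type 1 error is maintained". Both the intersection null (no effect in the full group and none in recent MI) and at least one individual null must be rejected at one-sided 0.025. It adds: "The results of the tests of the individual hypotheses (also at the one-sided 0.025 significance level) determines which specific comparisons are significant".

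SAP Section 9 gives the mechanics and points back to Section 2.3.5: "A closed testing procedure will be used for the primary efficacy analysis only".

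- **Step 1** takes p_f and p_s from least-squares means comparisons.
- **Step 2** sets t_max to the larger of t_f and t_s, which "are the t-statistics from the full group and subgroup analyses in (1) above".
- **Step 3** estimates the correlation r by the ratio of the SDs of the two treatment-effect estimates.
- **Step 4** lets p_inter "be the p-value from the test of the intersection hypothesis using Dunnett's test; specifically" 1 − probnorm(t_max, t_max, r).

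Success needs p_inter < 0.025 and either p_f or p_s < 0.025, with the effect favouring CAP-1002.

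On the model, the SAP says "An unstructured covariance will be the default covariance structure" and "for analyses based on the mITT population, missing data will be addressed using ML". It names no df method and no variance estimator for the tests. It does not say whether the full-group and recent-MI contrasts come from one model or two. Protocol 9.5.2 also mentions a Dunnett intersection p-value without degrees of freedom and refers to an adaptive-design interim analysis plan for details. SAP Section 14 lists no deviations from the protocol.

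**The concern.** The statistics in step 2 have estimated standard errors, so under the null they follow t-like distributions. Dunnett's test allows for this through its degrees of freedom. The formula in step 4 does not: its only arguments are t_max, twice, and r. Reading three-argument probnorm as the bivariate normal distribution function, the intersection cut-off is the one for known variance, which is too low for these sample sizes.

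The individual t-tests do not make up the difference. Their one-sided 0.025 cut-offs are about 1.99 (90 df) and 2.02 (43 df), both below 2.18. The uncorrected intersection step therefore decides the verdict.

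Steps 1 to 4 are the only success rule for the primary endpoint, so the error rate of the trial's main claim is at stake. The excess arises under the global null. If only one of the two nulls is true, rejecting it still requires its own t-test to pass at 0.025.

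**Working it through.** **Inputs**

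- One-sided 0.025 for the intersection and individual tests (SAP 2.3.5).
- 2:1 allocation within stratum (SAP 5).
- Up to 103 randomized, 51-52 per stratum (Protocol 9.2), planned "to achieve up to 93 subjects with complete 12 month data" (Protocol Synopsis).
- SD 10 (SAP Table 1). The null error rate does not depend on it.
- Assumed analysed numbers per stratum: 31 v 15 (46 × 2 = 92, about the 93 completers) and 34 v 17 (51 × 2 = 102, about all 103, the ceiling for the mITT population).

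**The plan's own figure.** The SAP states more than 90% power at a total of 100. Simulating its rule under Table 1 gives 99.96%, so that lower bound is met.

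**Correlation at 31 v 15**

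- SE_s = 10 × √(1/31 + 1/15) = 3.145
- SE_f = 10 × √(1/62 + 1/30) = 2.224
- r = 2.224 / 3.145 = 0.707

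**Cut-offs.** Solving 1 − Φ₂(c, c; 0.707) = 0.025 gives c = 2.178. The t-value with the same one-tail area is 2.214 at 90 df (full group, 92 − 2) and 2.252 at 44 df (recent MI, 46 − 2). As written, both statistics are held to 2.178.

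**Is the missing df the cause?** With known variance, P(max > 2.178) is 2.5%, as promised. Dividing the same pair of normals by a shared √(χ²/df) gives 2.72% at 88 df, 2.70% at 98 df and 2.93% at 43 df.

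**Family-wise error of the full rule under the global null.** The simulation used normal outcomes, equal strata and r = SE_f/SE_s recomputed in each trial, with p_f and p_s as one-sided t-tests at 0.025. There were 4,000,000 trials per design (Monte Carlo SE about 0.01 percentage points), and 1,000,000 for the baseline-adjusted column.

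| Variance and rule | Per stratum | One pooled model | Separate models | Separate, baseline-adjusted |
|---|---|---|---|---|
| df-corrected, SAP rule | 31 v 15 | 2.70% | 2.88% | 2.90% |
| df-corrected, SAP rule | 34 v 17 | 2.68% | 2.84% | 2.84% |
| df-corrected, each t converted to z | 31 v 15 | 2.48% | 2.55% | 2.56% |
| df-corrected, each t converted to z | 34 v 17 | 2.49% | 2.54% | 2.54% |
| df-corrected, bivariate t with pooled df | 31 v 15 | 2.49% | 2.63% | – |
| df-corrected, bivariate t with pooled df | 34 v 17 | 2.50% | 2.62% | – |
| ML divisor, SAP rule | 31 v 15 | 3.02% | 3.13% | 3.29% |
| ML divisor, SAP rule | 34 v 17 | 2.97% | 3.06% | 3.18% |

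The baseline-adjusted column stands in for the mixed model. With complete data, unstructured covariance, and treatment and baseline each crossed with visit (an assumption), the month-12 contrast equals this ANCOVA.

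The ML rows apply only if ML-divisor variances were used. The SAP does not specify that; it invokes ML for missing data.

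**Sensitivity to unequal strata** (93 analysed, separate baseline-adjusted fits): 3.0% if one third are recent MI and 2.8% if two thirds are.

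**The case against.** **Sidedness.** This is the strongest point. SAP Section 7.3 makes tests two-sided unless Sections 8-10 say otherwise, and Section 9 never says one-sided. The proviso that the effect must favour CAP-1002 is redundant for one-sided p-values and needed for two-sided ones. If p_f and p_s were two-sided p-values compared with 0.025, the individual tests would decide (cut-off 2.32 at 43 df) and family-wise error would be about 2.1% to 2.2%, within the promise. However, Section 9 points to Section 2.3.5, which says explicitly that the individual tests are one-sided at 0.025. The two-sided reading contradicts that sentence. What stands is that Section 9 should repeat the sidedness.

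**Unseen documents.** The interim analysis plan and the methods paper cited for the closed test were not available, and the plan may name a df method and a variance estimator. That is a fair caveat, but Section 9 gives an explicit formula with no place for degrees of freedom and defers to nothing.

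**Simplified model.** The simulation uses complete month-12 data and normal errors. A random-intercept model pooling residual information over months 6 and 12 would bring separate fits to about 2.7% to 2.8% (within-subject correlation 0.3 to 0.7, an assumption). The excess shrinks slightly but remains, and the SAP's default covariance is unstructured.

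**Size.** The excess is 0.2 to 0.4 percentage points in a Phase I/II trial, and with separate models the repair itself leaves about 2.55%. Both are true. They limit the importance of the point, but the rule still does not deliver the rate the plan sets.

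**Conclusion.** The concern holds. On the one-sided reading in Section 2.3.5, with df-corrected variances and equal strata, the closed test as written has a family-wise error of about 2.7% (pooled model) or 2.8% to 2.9% (separate models) against the stated 2.5%.

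The practical reach is narrow. At r of about 0.707, the verdict changes only when the deciding t-statistic lies between 2.18 and about 2.21 (full group, 90 df) or 2.25 (recent MI, 44 df). For example, a recent-MI t of 2.20 with a lower full-group t passes as written and fails once degrees of freedom are used. It should be corrected before database lock because it is the primary success rule and the correction is nearly free.

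**What to change.** In SAP Section 9:

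1. Convert t_f and t_s to z through their own degrees of freedom, z = Φ⁻¹(F_df(t)), where F_df is the t distribution function, and apply the bivariate normal step to the larger z.
2. Name the df method and a REML-type variance estimator.
3. State whether the two contrasts come from one model or two. A bivariate t with a single df is adequate only if both come from one pooled model; with separate models it leaves about 2.6%.
4. As clarifications, state that t is signed so that CAP-1002 benefit is positive (the alternative in Section 2.3.5 is a negative difference), and repeat that p_f and p_s are one-sided.

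The cost is one line of code and a short paragraph. The intersection cut-off rises from 2.18 to about 2.21 in a pooled model, or to 2.21 (full group) and 2.25 (recent MI) with separate models. Power at 31 v 15 per stratum under Table 1 is 99.89% to 99.90% before and 99.86% to 99.88% after. If the true effect were half of Table 1 (an assumption), it would fall from 71.4% to 70.1% (pooled) or from 71.6% to 69.7% (separate).

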## 9.1 MRI Parameters

MRI data will be delivered in a raw file provided by the MRI Core Lab and will include the following parameters:

- LVEF
- LVESV, LVEDV indexed to BSA
- Infarct size as a percent of LV mass (primary efficacy endpoint)
- Infarct size in grams
- Viable mass in grams, equal to total LV mass minus non-viable mass
- Regional wall motion

Regional wall motion will be analyzed using average (over slices) percent scar tissue (i.e., scar size), percent non-viable tissue, end diastolic wall thickness, end systolic wall thickness, and wall thickening. The region of IP administration will be assumed to be the region of the index MI. Sixteen-segment data correspond to region as follows:

- Left anterior descending artery = segments 1, 2, 7, 8, 13, and 14
- Left circumflex artery = segments 5, 6, 11, 12, and 16
- Right coronary artery = 3, 4, 9, 10, and 15

Index MI locations reported for subjects with different coronary anatomy will be associated with specific segments on a case-by-case basis. Analysis parameters will be observations averaged over the involved segments for the index location. For example, if the index location is the right coronary artery, wall thickening for the index location will be the mean “average” wall thickening over segments 3, 4, 9, 10, and 15.

Regional wall motion will also be analyzed within the following locations:

- Anterior = 1, 7, and 13
- Lateral = 5, 6, 11, 12 and 16
- Inferior = 4, 10, and 15
- Septal = 2, 3, 8, 9, and 14

Of note, segments 2 and 3 will be excluded for wall thickness and wall thickening analyses.

Scar transmurality will be defined as number of segments with > 0% non-viable tissue.

For each parameter, the observed value, absolute change from baseline, and percent change from baseline (except for scar transmurality) will be listed and summarized. Summary tables will include p-values for treatment group comparisons of changes from baseline. For the primary efficacy endpoint, p-values for the intersection hypothesis as well as the subgroup hypotheses (see [Section 2.3.5](#)) will be presented.

Details from the MRI procedure collected on the CRF will be listed.

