
4. Left ventricular infarct size of $\geq 15\%$ of left ventricular mass in the qualifying infarct-related region to be infused as determined by centrally read screening MRI, with associated thinning and/or hypokinesis, akinesis, or dyskinesis, with no large aneurysmal area in the infarcted regions.
5. No further revascularization clinically indicated at the time the subject is assessed for participation in the clinical trial.
6. Ability to provide informed consent and follow-up with protocol procedures.
7. Age ≥ 18 years.

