9.6.2 Secondary Efficacy

All comparisons in the secondary analyses will be based on a null hypothesis of no difference in the endpoint between subjects administered CAP-1002 as compared to placebo and an alternate hypothesis of a difference in the endpoint for subjects administered CAP-1002 as compared to placebo. Secondary analyses will be based on a random effects model similar to the primary but will be based on an alpha of 0.05 without controlling for multiplicity.

The following secondary efficacy endpoints will be evaluated during the six-month and twelve-month follow-up periods:

Global LV Function measures

1. Percent change and change from baseline in MRI assessment of LVEF
2. Percent change and change from baseline in MRI assessment of left ventricular end-diastolic and end-systolic volumes indexed to BSA

Structural measures

3. Change from baseline in MRI assessment of infarct size as a percent of left ventricular mass
4. Percent change and change from baseline in MRI assessment of infarct size expressed in grams
5. Percent change and change from baseline in MRI assessment of viable mass expressed in grams

Regional measure

6. Percent change and change from baseline in MRI assessment of function in the region which received CAP-1002 therapy

Clinical function/status measures

7. Changes from baseline in distance covered in six minute walk test

8. Change from baseline in Minnesota Living with Heart Failure Questionnaire (MLHFQ) score
9. Change from baseline in SF-36 score
10. Change from baseline in WPAI:SPH score
11. Change from baseline in Patient Global Assessment (PGA) score
12. Change from baseline in NYHA Class

Biomarker

13. Percent change and change from baseline in NT-proBNP
14. Change from baseline in log transformed NT-proBNP

Additional detail regarding secondary endpoint analyses can be found in the SAP.

Analyses of the secondary efficacy endpoints will be performed using the same longitudinal modeling approach as the primary efficacy endpoint; the baseline covariate used in the model will be the baseline of the endpoint being analyzed. Two-sided testing will be performed at level $p=0.05$.

A correlational analysis will be presented (for tissue based and functional measures) with Pearson's correlation coefficient for all possible pairs of efficacy endpoints and where appropriate the Spearman's correlation coefficient will be presented.

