### 2.3.6 Secondary Efficacy Endpoints

The following secondary efficacy endpoints will be evaluated at 6 and 12 months post IP administration unless otherwise noted:

1. Absolute and relative change from baseline in global LV function measures:
  - a) MRI assessment of LV ejection fraction (LVEF)
  - b) MRI assessment of LV end diastolic volume (LVEDV) and end systolic volume (LVESV) indexed to body surface area (BSA)
2. Absolute and relative change from baseline in structural measures:
  - a) MRI assessment of infarct size as a percent of LV mass
  - b) MRI assessment of infarct size expressed in grams
  - c) MRI assessment of viable mass expressed in grams
  - d) MRI assessment of scar transmurality
3. Absolute and relative change from baseline in regional measures:

- a) MRI assessment of function and structure by segment or groups of segments (e.g., region which received the IP)
- 4. Absolute change from baseline in clinical function/status measures:
  - a) Distance covered in six minute walk test (6MWT)
  - b) Minnesota Living with Heart Failure Questionnaire (MLHFQ) score
  - c) Patient Global Assessment (PGA) score
- 5. Absolute and relative change from baseline in cardiac biomarkers:
  - a) NT-proBNP

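### SAP 9.1 tests percent change in regional wall thickening, whose baseline can be near zero or negative in some subjects; its RCA segment example also contradicts a later exclusion

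*SAP*

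**What the plan says.** SAP 9.1 lists the regional measures as percent scar, percent non-viable tissue, "end diastolic wall thickness, end systolic wall thickness, and wall thickening". Each is averaged over the segments of the index-MI territory and analysed again in four fixed locations (anterior, lateral, inferior, septal). For each MRI parameter the section then asks for the observed value, the absolute change and "percent change from baseline (except for scar transmurality) will be listed and summarized", and adds that "Summary tables will include p-values for treatment group comparisons of changes from baseline". Scar transmurality is the only exception.

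Both documents make this a secondary efficacy endpoint. SAP 2.3.6 item 3 reads "Absolute and relative change from baseline in regional measures". Protocol 9.6.2 item 6 reads "Percent change and change from baseline in MRI assessment of function in the region which received CAP-1002 therapy", and the same line appears in the protocol synopsis and in 2.4.1.

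Protocol 4.2, inclusion criterion 4, requires an infarct of at least 15% of LV mass in the region to be infused, "with associated thinning and/or hypokinesis, akinesis, or dyskinesis". Neither document gives a unit, a formula or an expected distribution for wall thickening, or a rule for a zero, near-zero or negative baseline.

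On segments, SAP 9.1 illustrates the averaging with the right coronary artery (RCA), taking the mean of "wall thickening over segments 3, 4, 9, 10, and 15". Later in the section it notes that "segments 2 and 3 will be excluded for wall thickness and wall thickening analyses".

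**The concern.** Percent change has a fixed meaning only when the baseline is positive and well away from zero. Akinetic myocardium does not thicken in systole, and dyskinetic myocardium can thin. A territory containing enough of either can have a mean baseline thickening at or below zero. For such a subject a recovery enters the percent-change analysis as a loss and a deterioration as a gain. For a subject with a small positive baseline, an ordinary change becomes a value of several hundred percent. The treatment comparison of percent change could then be dominated by a few denominators, and the table could print a p-value whose direction cannot be read.

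A related gap affects scar and non-viable tissue. A fixed location away from the infarct may contain neither at baseline, and percent change from zero is undefined. SAP 9.1 anticipates segments at 0%, because it defines transmurality by counting the segments above 0% non-viable tissue.

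The segment conflict matters because the RCA mean for thickening has two possible values under the text as written.

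**Working it through.** The documents state no power, effect size or expected value for regional thickening, so there is no planned figure to reproduce.

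**1. Behaviour of percent change.** With baseline B and follow-up F, percent change = 100 × (F − B)/B.

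| B | F | Absolute change | Percent change |
|---|---|---|---|
| 20 | 25 | +5 | +25% |
| 1 | 6 | +5 | +500% |
| 0.5 | 5.5 | +5 | +1000% |
| 0 | 5 | +5 | undefined |
| −1 | 4 | +5 | −500% |
| −5 | 5 | +10 | −200% |
| −5 | −10 | −5 | +100% |

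The first five rows are the same gain of 5. Dividing by |B| would restore the sign (−5 to +5 becomes +200%) but would not tame the near-zero rows.

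**2. Possible effect on the test.** From the documents: 93 completers at 2:1, so 93 × 2/3 = 62 against 31; a baseline-adjusted linear model (SAP 9); two-sided 0.05 (protocol 9.6.2). Assumed: normal baseline, SD of change equal to the baseline SD, change independent of baseline apart from treatment, true effect 0.7 SD, a single follow-up visit. The unknown, baseline mean/SD, is varied. There were 3,000 runs per row, and power is counted in the correct direction.

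| Baseline mean/SD | Baselines ≤ 0 | Power, absolute | Power, percent | Percent-change estimate has wrong sign |
|---|---|---|---|---|
| 5 | 0% | 89% | 87% | 0.1% of runs |
| 3 | 0.1% | 88% | 70% | 3% |
| 2 | 2.3% | 88% | 26% | 19% |
| 1 | 15.9% | 88% | 4.5% | 36% |
| 0.5 | 30.9% | 88% | 2% | 45% |
| 0 | 50% | 87% | 1% | 51% |

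A second set of assumptions (baseline SD 15, SD of change 10, benefit 5 points; 2,000 runs) gives the same pattern. Power for percent against absolute change is 56% against 59% at baseline mean 60 (mean/SD 4) and 46% against 61% at mean 45 (mean/SD 3). At mean 30 (mean/SD 2) it is about 16% against 60%, and at mean 15 (mean/SD 1) about 4% against 60%.

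**3. Scar and non-viable tissue.** These cannot be negative, so F − B and its percent change always share a sign when B > 0. At B = 0 the ratio does not exist. In the index territory, inclusion criterion 4 ensures that baseline scar is positive. In the four fixed locations nothing does.

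**4. Segments.** Counts as listed, and after dropping 2 and 3:

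| Average | As listed | With 2 and 3 excluded |
|---|---|---|
| RCA | 3, 4, 9, 10, 15 (5) | 4, 9, 10, 15 (4) |
| LAD (left anterior descending) | 1, 2, 7, 8, 13, 14 (6) | 1, 7, 8, 13, 14 (5) |
| Septal | 2, 3, 8, 9, 14 (5) | 8, 9, 14 (3) |

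The circumflex, anterior, lateral and inferior lists contain neither segment. The worked RCA example is for wall thickening and uses segment 3, so it conflicts directly with the exclusion. As an invented illustration, if segment 3 is 0 and the other four are 20, the RCA mean is 80/5 = 16 or 80/4 = 20. If segment 3 is −30 and the others 5, it is (−30 + 20)/5 = −2 or 20/4 = 5, so the choice can change the sign of the denominator.

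**The case against.** The strongest reply is that the faulty denominators may be rare. A reader might infer that entry requires akinetic or dyskinetic myocardium and that baselines therefore generally sit near or below zero. The documents do not support that. The and/or in criterion 4 lets thinning alone qualify, hypokinesis is reduced but still positive thickening, and the analysed value is a mean over five or six segments as listed. If baselines lie four or five SDs above zero, percent change loses almost nothing. This stands: frequency and impact are unknown, and it cannot be said that the percent-change test is generally uninformative.

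A reader might also infer that percent scar shares the sign reversal. It does not. Its only difficulty is the undefined value at zero, and only in the four-location analysis.

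Or a reader might see the LAD and septal lists as contradictory too. They are better read as general lists, used for all regional measures, with a stated exception for thickness and thickening. Only the RCA example conflicts with that exception.

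Finally, SAP 9 provides residual checks, transformations and alternative approaches, absolute change is already analysed, and secondary tests carry no multiplicity control or success claim. This limits the consequence. It does not repair the rule: neither a baseline covariate nor a residual-driven remedy corrects a response whose sign is reversed, and remedies chosen after looking at residuals are not a rule for the denominator.

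**Conclusion.** The point holds in limited form. As written, the plan tests percent change in a measure that can be zero or negative in some of the subjects it admits, with no rule for those cases. The sign reversal and the undefined values are arithmetic and need no assumption beyond such a baseline occurring. How often that happens cannot be determined from the documents. Under the assumed inputs the cost in power runs from about 2 points (89% to 87%) at a baseline mean/SD of 5 to nearly all of it (88% to 4.5%) at 1.

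The gap for scar and non-viable tissue is confined to fixed locations with 0% at baseline. The segment contradiction is certain but confined to the RCA example.

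This concerns a secondary endpoint. The primary endpoint, percent change in infarct size as a percent of LV mass, is not affected, because entry at 15% or more keeps its denominator positive. The point merits correction because a printed p-value could otherwise point the wrong way and the remedy is nearly free.

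**What to change.** - In SAP 9.1 and SAP 2.3.6 item 3, and in the protocol's regional-measure lines (synopsis, 2.4.1 and 9.6.2 item 6), analyse wall thickening by absolute change only, extending the exception already made for scar transmurality. State its unit and formula.
- In the four-location analysis, use absolute change only for percent scar and percent non-viable tissue. Percent change may stay for scar in the index territory.
- Reconcile the RCA example with the exclusion of segments 2 and 3, and list the segments used for thickness and thickening. If the exclusion stands, these are RCA 4, 9, 10, 15; LAD 1, 7, 8, 13, 14; septal 8, 9, 14.

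The cost is wording in both documents and the loss of a percent-change column for a secondary endpoint. Absolute change is already planned, so no new data or analysis is needed. In the first simulation its power stays at 87% to 89% whatever the baseline, and its sign can always be read.
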